2 STUDY OBJECTIVES

2.1 Phase I

2.1.1 Primary Objective

To evaluate dose-limiting toxicities (DLTs) of combination treatment with itacitinib and everolimus occurring up to and during Day 28 of Cycle 1, and to establish a recommended Phase II dose (RP2D) in subjects with relapsed or refractory cHL.

2.1.2 Secondary Objective

The secondary objective of Phase I is to evaluate the efficacy of itacitinib in combination with everolimus in terms of CR, ORR, PR, SD, duration of response, PFS, and OS.

Version 11.0 Page 24 of 72

2.1.3 Exploratory Objective

To evaluate impact of itacitinib in combination with everolimus on QOL.

2.2 Phase II

2.2.1 Primary Objective

The primary objective of Phase II is to evaluate the efficacy of itacitinib in combination with everolimus in subjects with relapsed or refractory cHL as demonstrated by CR rate.

2.2.2 Secondary Objective

The secondary objectives of Phase II are as follows:

- To evaluate efficacy in terms of ORR, PR, SD, duration of response, PFS, OS.
- To evaluate the safety and tolerability of the treatment combination.

2.2.3 Exploratory Objective

To evaluate impact of itacitinib in combination with everolimus on QOL.

3 INVESTIGATIONAL PLAN

3.1 General Design

This is an open-label, single-group, Phase I/II study of itacitinib in combination with everolimus in subjects with relapsed or refractory cHL. Phase I will evaluate the safety and tolerability of itacitinib when combined with everolimus in subjects with relapsed refractory cHL using a 3 + 3 design; Phase II will evaluate the efficacy of the combination in subjects with cHL at the dose determined in Phase I using a Simon 2-stage expansion design. Subjects may continue to receive study treatment for 2 years or until evidence of disease progression, unacceptable toxicity, inability to obtain commercial everolimus or consent withdrawal. The number of cycles may be extended if sufficient data is provided by the manufacturer demonstrating safety of the itacitinib monotherapy and the subject continues to receive a clinical benefit.

3.1.1 Screening Phase

Subjects with relapsed/refractory cHL will be recruited from the practices at the University of Pennsylvania. Subjects will not be reimbursed for participation. After signing the ICF, screening assessments may be completed over a period of up to 28 days.

3.1.2 Study Intervention Phase I

Utilizing 3 + 3 design, 6 to 15 subjects will be enrolled to Phase I portion of the trial (with at least 6 subjects treated at RP2D). The starting dose of itacitinib will be 300 mg once daily (QD) in combination with everolimus 5 mg QD. Depending on tolerability, the dose of itacitinib in combination with everolimus could be increased to 400 mg QD (Cohort 2) or decreased to 200

Itacitinib + everolimus in HL
Version 11.0
Page 25 of 72

mg QD (Cohort -1). There will be no intra-patient dose escalations in phase I. The dose of everolimus will remain 5 mg QD for each cohort.

Additional subjects may be enrolled to achieve a minimum cohort size should withdrawal or dose interruptions/reductions result in a subject being non-evaluable. Dose cohorts are outlined in Table 1, and the design is depicted in Figure 1.

[figure not shown]
Subjects who experience a DLT or an unacceptable toxicity (i.e. not able to resume therapy within 28 days due to unresolved toxicity) beyond the DLT window will be also considered in the determination of the RP2D dose.

Table 1: Dose Cohort Design

Cohort	Subjects	Regimen	DLTs	Action
-1	0-6	Everolimus 5 mg QD	0/6	Begin Phase 2 at Cohort -1 dose
		itacitinib 200 mg QD	1/3	Enroll 3 additional subjects (6 total) at Cohort - 1 level; if no additional DLT, begin Phase 2 at Cohort -1 dose; if 1 or more additional DLTs, terminate study
			≥ 2	Terminate study
1	3-6	Everolimus 5 mg QD	0/3	Escalate to Cohort 2 dose
(starting dose)		itacitinib 300 mg QD	1/3	Enroll 3 additional subjects (6 total) at Cohort 1; if no additional DLT, begin Phase 2 at Cohort 1 dose; if 1 or more additional DLTs, de-escalate to Cohort -1
			≥ 2	De-escalate to Cohort -1
2	0-6	Everolimus 5 mg QD	0/6	Begin Phase 2 at Cohort 2 dose
		itacitinib 400 mg QD		Enroll 3 additional subjects at Cohort 2 (6 total);
			1/3	if no additional DLT, begin Phase 2 study at Cohort 2 dose; if 1 or more additional DLTs, treat 3 more patients on Cohort 1 dose, if 0-1 DLTs on Cohort 1, then RP2D is Cohort 1, if ≥ 2 DLTs on Cohort 1, then de-escalate and treat 6 patients at Cohort -1; if 0-1/6 have DLTs – the RP2D is Cohort -1, if ≥ 2 DLTs, then study is terminated
			≥ 2	Treat 3 more patients on Cohort 1 dose (6 total), if 0-1 DLTs on Cohort 1, then RP2D is Cohort 1, if $\geq 2/3$ DLTs on Cohort 1, then reduce to Cohort -1 and treat 6 patients. If 0-1/6 of Cohort -1 have DLTs – then RP2D is Cohort -1, if ≥ 2 DLTs, then study is terminated

Version 11.0 Page 26 of 72

Figure 1: Dose Cohort Design

^{*:} must treat 6 patients at RP2D before proceed to Phase I

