	To evaluate dose-limiting toxicities (DLTs) of combination treatment with itacitinib and everolimus occurring up to and during Day 28 of Cycle 1, and to establish a recommended Phase II dose (RP2D) in subjects with relapsed or refractory cHL.		
	Secondary Objective		
	To evaluate efficacy of itacitinib in combination with everolimus in terms of ORR, CR, PR, SD, duration of response, PFS, OS.		
	Exploratory Objective		
	To evaluate impact of itacitinib in combination with everolimus on QOL.		
	PHASE II		
	Primary Objective		
	To evaluate the efficacy of itacitinib in combination with everolimus in subjects with relapsed or refractory cHL as demonstrated by CR rate.		

Page 13 of 72

	Secondary Objectives		
	To evaluate efficacy in terms of ORR, PR, SD, duration of response, PFS, OS.		
Т	To evaluate the safety and tolerability of the treatment combination.		
	•		
	To evaluate impact of itacitinib in combination with everolimus on QOL.		
NT 1 C	•		
and Exclusion Criteria 2.3.4.	Up to 28 patients will be enrolled for planned 23 evaluable subjects n MAIN INCLUSION CRITERIA:		

Itacitinib + everolimus in HL
Version 11.0
Page 14 of 72

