4.5 Total Number of Subjects and Sites

The total planned number of evaluable subjects at UPenn will be 23 (including those in Phase I and II portions). To complete Phase I portion utilizing the 3 + 3 design, it is expected that 6 to 12 subjects will be enrolled. For phase II, 11 to 17 subjects will be enrolled. It is expected that total of 17-20 subjects will be treated at the RP2D dose since 3 to 6 patients from Phase I will be treated under the same regimen as Phase II patients. In order to be included in the tolerability review of Phase I, subjects must have received the cohort-specific dose of itacitinib and everolimus for at least 75% of the days during the first 28-day surveillance period or have experienced a DLT. Up to 5 additional subjects may be enrolled to achieve a minimum cohort size should withdrawal or dose interruptions/reductions result in subjects being non-evaluable during Phase I.

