7 STATISTICAL PLAN

7.1 Sample size

Sample size determination: Utilizing 3 + 3 design, 6 to 15 subjects will be enrolled to Phase I portion of the trial (with at least 6 subjects treated at RP2D). Phase II will enroll 8 to 17 subjects depending on expansion needs in the Phase I portion. At least 14 subjects will be treated at RP2D level and evaluable for CR rate. The sample size for phase II was based on a decision between 2 pre-specified hypotheses about the probability of CR rate (p). The null hypothesis H₀: p = 5% reflects a response rate that would be of no clinical benefit compared to everolimus alone, and the alternative hypothesis H_a: p = 25% is a CR rate that might lead to larger, confirmatory studies. Using a Simon 2-stage optimal design, a total of 17 subjects at RP2D will be needed for 80% power at 1-sided alpha = 0.05 level. If by the 16 week visit there are no responders with CR from the first 9 evaluable subjects (at any itacitinib dose level), the null hypothesis will be considered as supported, and the study will be terminated.

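### Table 1 can require 18 evaluable Phase I subjects, but the plan states a maximum of 15 (12 expected in 4.5), and the planned totals do not allow for it

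*Combined protocol and SAP*

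**What the plan says.** All references are to the combined protocol and SAP.

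- **Phase I size.** Section 3.1.2: "Utilizing 3 + 3 design, 6 to 15 subjects will be enrolled to Phase I portion of the trial". Section 7.1 repeats it ("6 to 15 subjects will be enrolled to Phase I"), as does the statistical part of the Study Summary. Section 4.5 differs: "it is expected that 6 to 12 subjects will be enrolled".
- **Cohort rules (Table 1 in 3.1.2).** With 0/3 DLTs at Cohort 1 the action is "Escalate to Cohort 2 dose". With 1/3 at Cohort 2, that cohort is expanded to 6. The row continues "if 1 or more additional DLTs, treat 3 more patients on Cohort 1 dose", and then "if ≥ 2 DLTs on Cohort 1, then de-escalate and treat 6 patients at Cohort -1". The Subjects column allows up to 6 in each of the three cohorts.
- **Totals.** Study Summary: "Up to 28 patients will be enrolled for planned 23 evaluable subjects". Section 4.5 confirms that the 23 spans both phases and allows up to 5 extra subjects to replace those not evaluable in Phase I.
- **Phase II.** Section 7.1 needs 17 at the RP2D for 80% power. Sections 3.1.3 and 7.1 also give Phase II as 8 to 17 subjects, with a floor of 14 evaluable at the RP2D. Section 3.1.3 counts 6 Phase I subjects towards Phase II. Section 4.5 gives 11 to 17 in Phase II, 17 to 20 at the RP2D, and 3 to 6 carried over.

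**The concern.** The upper limit of a 3+3 range should be the longest path that the cohort rules allow. Here it is not: one branch written in Table 1 runs past both 15 and 12. The replacement allowance does not close the gap, because it covers non-evaluable subjects and all 18 on this path are evaluable.

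The planning totals depend on the Phase I count. If Phase I runs longer than assumed, the planned 23 evaluable subjects leave fewer for the RP2D group on which the primary CR rate is tested. The plan should state a ceiling that holds on every path it prescribes, and the same ceiling in every section.

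**Working it through.** **1. Where 15 comes from.** Cohort 1 has 0/3 (3 subjects), Cohort 2 fails within its first 3 (3), 3 more are treated at Cohort 1 (3), and 6 at Cohort -1 (6): 3 + 3 + 3 + 6 = 15. So 15 is the maximum only if Cohort 2 is never expanded.

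**2. The written 1/3 branch at Cohort 2.**

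| Step | Added | Running total |
|---|---|---|
| Cohort 1, 0/3 DLTs | 3 | 3 |
| Cohort 2, 1/3 DLTs | 3 | 6 |
| Cohort 2 expanded, at least 1 more DLT | 3 | 9 |
| Back to Cohort 1, at least 2 DLTs | 3 | 12 |
| Cohort -1 | 6 | 18 |

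This is 6 in each of three cohorts, in line with the Subjects column. It exceeds 15 by 3 and 12 by 6. If Cohort -1 is staged as in its own row (3, then 3), 18 is still reached unless 2 or more of its first 3 subjects have DLTs; in that case the study stops at 15.

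**3. How often.** The documents give no DLT rates, so these are assumptions (200/300/400 mg). Write p1 for the rate at 300 mg and p2 for the rate at 400 mg. For the written branch, with 6 treated at Cohort -1:

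P(18) = (1 − p1)³ × 3·p2·(1 − p2)² × [1 − (1 − p2)³] × [3·p1²·(1 − p1) + p1³]

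- 10/20/30%: 0.512 × 0.441 × 0.657 × 0.104 = 0.0154
- 15/30/45%: 0.343 × 0.4084 × 0.8336 × 0.216 = 0.0252
- 20/35/50%: 0.2746 × 0.375 × 0.875 × 0.2818 = 0.0254

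So about 1.5% to 2.5%. Adding paths where Cohort 2 has 0/3 and then 2 or more of 3 raises these to 1.9%, 3.1% and 3.0%. Table 1 states no action for that outcome, so I do not rely on the higher figures. The maximum of 18 does not depend on it.

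**4. Totals.** Evaluable total = Phase I number − 6 carried over + number at the RP2D.

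| Phase I | RP2D = 17 | plus 5 replacements | RP2D = 14 | plus 5 replacements |
|---|---|---|---|---|
| 12 | 23 | 28 | 20 | 25 |
| 15 | 26 | 31 | 23 | 28 |
| 18 | 29 | 34 | 26 | 31 |

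The stated 23 and 28 are reproduced in two cells: 12 in Phase I with 17 at the RP2D, or 15 in Phase I with only 14 at the RP2D. They are not reproduced with 15 and 17 together, nor with 18 and either RP2D figure.

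**5. The same sum in reverse.** RP2D number = total − Phase I number + 6. From 23 evaluable, 15 in Phase I leaves 14 and 18 leaves 11, below the floor of 14. From 28, if all were evaluable, 18 leaves 16, one short of 17.

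**6. The input of 17.** An exact search for the optimal two-stage design at 5% against 25%, with 80% power and one-sided 0.05, gives 9 subjects in stage 1 and 17 in all. The total of 17 is not in question.

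**The case against.** The strongest reply is that the plan is more flexible than a single total suggests. Phase II is 8 to 17 subjects depending on Phase I expansion, with a floor of 14 at the RP2D. On that reading 15 + 8 = 23 matches the plan, and 18 + 8 = 26 fits within 28. This stands in part. A reader might infer that 28 cannot accommodate the cohort scheme at all. The documents do not support that: 28 is exceeded before replacements only with 17 at the RP2D, and then by one subject. With the floor of 14, the 18-subject path leaves room for 2 of the 5 replacements. The floor does not rescue the planned 23, which is exceeded on that path either way, and it sits beside the statement in 7.1 that 17 are needed for 80% power.

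A reader might also infer that the team would be left to improvise once 15 subjects were treated. That does not follow. Table 1 says what to do on this path, no section calls 15 an approved limit, and 18 is well below 28. Likewise the 12 in 4.5 is worded as an expectation, not a cap.

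Finally, the path is improbable. Reaching 29 evaluable is rarer still, because Cohort -1 must also pass and at least one of the first 9 evaluable subjects must have a CR. That limits the practical weight of the point, not its correctness.

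**Conclusion.** The point holds as an inconsistency in the enrolment figures. The Phase I maximum under Table 1 is 18 evaluable subjects, against 15 in the Study Summary, 3.1.2 and 7.1 and 12 expected in 4.5. This is a count from the written rules and needs no assumption.

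The effect on the totals depends on which RP2D figure governs. With 17, the evaluable total is 26 when Phase I uses 15 and 29 when it uses 18, against 23 planned and 28 enrolled. With 14, the 18-subject path needs 26, which exceeds 23 but not 28. Both results use the 6 subjects carried over in 3.1.3.

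The 1.5% to 2.5% chance of needing 18 rests on assumed DLT rates and on the written 1/3 branch alone. Nothing here shows an error in the Simon sample size or calls for a change to the escalation rules. The correction is worth making because the figures contradict each other whichever path occurs, and correcting them costs little.

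**What to change.** - Restate Phase I as 6 to 18 evaluable subjects in the Study Summary, 3.1.2, 4.5 and 7.1.
- If 17 at the RP2D is kept, state the maximum evaluable total as 29 (18 − 6 + 17). State the replacement allowance separately, so that the enrolment ceiling is visibly the sum of the two.
- Reconcile the dependent Phase II figures with 17 at the RP2D and 6 carried over, which means 17 − 6 = 11 new Phase II subjects. The figures concerned are the 8 to 17 in the Study Summary, 3.1.3 and 7.1 (the Study Summary attaches it to the total treated at the RP2D, the other two to Phase II enrolment), the floor of 14 in 3.1.3 and 7.1, and the 11 to 17, 17 to 20 and 3 to 6 in 4.5. If the floor of 14 is meant to stay, say when it applies.

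The cost is text corrections and a revised enrolment ceiling. No subjects are added on paths that the present figures already cover.

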3.1.3 Study Intervention Phase II

Subjects with cHL will receive the recommended Phase II dose (RP2D) of itacitinib in combination with everolimus as determined in Phase 1. Phase II will enroll 8 to 17 subjects depending on Cohort expansion in the Phase I portion. Since 6 of the Phase I subjects will be recruited, treated and followed in the same way as the Phase II subjects, they will be considered as accrued to the Phase II study as well. At least 14 subjects will be treated at RP2D level and evaluable for CR rate. Using a Simon 2-stage optimal design, if there are no responders with CR by the 16 week response assessment from the first 9 evaluable subjects at the RP2D, the null hypothesis will be considered as supported, and the study will be terminated. If there are no CRs in the first several patients (week 8 or 16 assessment), we will suspend the study enrollment and await final response assessment on all 9 patients (until week 16). The study will be considered successful if the total number of subjects with CR is \geq 2 in Phase II.

3.1.4 Follow Up Phase

Subjects who discontinue treatment for any reason will be followed for resolution of treatment-related adverse events and survival. At treatment discontinuation, subjects will undergo a safety assessment approximately 28 days post the last dose of protocol therapy. Subjects will be

Itacitinib + everolimus in HL

Version 11.0 Page 27 of 72

followed for additional therapy and progression/survival data every three months (+/- 1 month) for the first year and every 6 month (+/- 1 month) for the second year after study discontinuation.

3.1.5 Allocation to Interventional Group

Patients who sign ICF will be assigned a 7 digit number. First 5 digits will be the study UPCC number and the last 2 digits will be the subject's number. This subject number will be maintained throughout the study and will not be reassigned. Subjects who withdraw consent or discontinue from the study after being assigned a subject number will retain their initial number. During Phase I, subjects will be assigned to specific itacitinib dose Cohort as described in Table 1/Figure 1. For Phase II, subjects will be treated at the RP2D determined in Phase I.

3.2 DLT Definition

A DLT will be defined as the occurrence of any toxicities in Table 2 occurring up to and including Day 28 of Cycle 1, except those with a clear alternative explanation (e.g., disease progression) or transient (≤ 72 hours) abnormal laboratory values without associated clinically significant signs or symptoms based on investigator and sponsor determination. All DLTs will be assessed by the investigator using CTCAE v5 criteria (NCI 2018). In order to be included in the tolerability review, subjects must have received the cohort-specific dose of itacitinib and everolimus for at least 75% of the days during the 28-day surveillance period of Cycle 1 or have experienced a DLT.

Individual subject dose reductions may be made based on events observed at any time during treatment with study drug (see Section 5.6); however, for the purposes of dose cohort escalation/de-escalation, expanding a dose cohort, and determining the RP2D, decisions will be made based on events that are observed from the first day of study drug administration through and including Day 28. A lower RP2D may subsequently be determined based on relevant toxicities that become evident after Day 28.

Subjects who experience a DLT or an unacceptable toxicity (i.e. not able to resume therapy within 28 days due to unresolved toxicity) beyond the DLT window will be also considered in the determination of the RP2D dose.

Any grade 5 hematologic and non-hematologic event related to the study treatments (at any time) will be considered a DLT.

Table 2: DLT defining toxicities

TOXICITY

Non-hematologic

- Any \geq Grade 3 non-hematologic toxicity, EXCEPT the following:
 - Transient (≤ 72 hours) abnormal laboratory values without associated clinically significant signs or symptoms.
 - Nausea, vomiting, and diarrhea adequately controlled with medical therapy within 48 hours.

Itacitinib + everolimus in HL
Version 11.0
Page 28 of 72

 Singular or non-fasting elevations in blood glucose (i.e., blood glucose excursions will be considered toxicities if fasting blood glucose is elevated on 2 separate sequential occasions).

Hematologic

- Grade 3 thrombocytopenia with bleeding.
- Grade 4 thrombocytopenia.
- Febrile neutropenia (ANC $< 1.0 \times 10^9$ /L and fever $> 101^\circ F/38.5^\circ C$).
- Grade 4 neutropenia that does not recover to \leq Grade 2 in \leq 3 days after interrupting study drug.
- Grade 4 anemia unresponsive to treatment for 3 days

Note: itacitinib is suspected to cause transient decreases in ANC as a result of margination; therefore, DLT rules require neutropenia to persist after holding itacitinib for 3 days. The use of growth factors is permitted at the discretion of the investigator. If the clinical status of the subject allows, investigators are encouraged to wait 24 hours before starting growth factors, to determine if WBC margination is contributing to the degree of neutropenia.

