1.3.2 Everolimus

Everolimus selectively inhibits mTOR a highly conserved serine-threonine kinase, which is present in all cells and is a central regulator of protein synthesis. mTOR is the only currently known target of everolimus. mTOR is downstream of PI3K/AKT pathway, a pathway known to be dysregulated in a wide spectrum of human cancers including cHL.

Everolimus is rapidly absorbed with a median t_{max} of 1-2 hours. The bioavailability of the drug is believed to be 11% or greater. The AUC_{0- τ} is dose-proportional over the dose range between 5 to 70 mg in the weekly regimen. Steady-state levels were achieved within two weeks of once daily dosing. There was no evidence of increased oncogenesis in rats and mice at 0.2 and 4.3-times, respectively, the estimated clinical exposure for Renal Cell Carcinoma patients. Additionally, in rats, everolimus was found to cross the placenta and adversely affect male

Page 20 of 72

fertility at 0.5mg/kg doses and above. Accordingly, inclusion criteria require both male and female subjects to use contraception. Everolimus is a substrate of CYP3A4 and a substrate and moderate inhibitor of Pg. Following oral administration, everolimus is the main circulating component in human blood and is considered to contribute the majority of the overall pharmacologic activity.

In a recently published Phase II study of everolimus monotherapy (10mg daily, oral, 28 day cycles) in relapsed/refractory NHL, hematologic toxicity was most frequently observed (Gr 3/4 anemia (15%; 8/55), neutropenia 12%; (12/55), and thrombocytopenia (33%; 18/55); febrile neutropenia was not observed and 8/55 discontinued therapy because of adverse events. The authors concluded that everolimus monotherapy was safe and effective (ORR 35% (19/55) overall and 61% (14/23) for FL) [15]. Age, weight and gender in the adult population do not affect everolimus clearance. For more information, refer to the package insert.

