•	\geq Grade 3 ANC with an oral temperature of at least 38.5°C OR with \geq Grade 3 infection. Platelet count is $< 35 \times 10^9/L$	Step 2: Restart itacitinib and everolimus at same dose, if unrelated. If assessed as related to itacitinib, restart at next lower dose. If assessed as related to everolimus, restart at the next lower dose. Monitor as clinically indicated.			

Itacitinib + everolimus in HL
Version 11.0
Page 37 of 72

	ADVERSE EVENT	ACTION TAKEN
O	THER	
•	Any Grade 1 or Grade 2 toxicity	Continue study treatment and treat the toxicity; monitor as clinically indicated.
•	Any Grade 3 toxicity, if clinically significant and not	Step 1: Interrupt itacitinib and/or everolimus up to 28 days until the toxicity has resolved to ≤ Grade 1.
	manageable by supportive care	Step 2: Restart itacitinib and/or everolimus at same dose if unrelated. If assessed as related to itacitinib, restart at next lower dose. If assessed as related to everolimus, restart at the next lower dose. Monitor as clinically indicated.
•	Any recurrent Grade 3 toxicity after dose reductions	Discontinue study itacitinib and/or everolimus administration. Exceptions require approval of sponsor.
•	Any other Grade 4 toxicity	Discontinue itacitinib and/or everolimus administration. Exceptions require approval of sponsor.

Table 4: Guidelines for Interruption and Restarting Study Drugs due to AEs suspected to result from everolimus

ADVERSE EVENT	ACTION TAKEN
	Non-infectious Pneumonitis ¹
Grade 1	No specific therapy is required Administer 100% of everolimus dose. However, depending on the clinical scenario,
	investigator may hold everolimus during the work-up.
Grade 2	Symptomatic only. Prescribe corticosteroids if cough is troublesome.
	Hold until recovery to \leq Grade 1. Subjects will be withdrawn from the study if they fail to recover to \leq Grade 1 within 28 days.
Grade 3	Prescribe corticosteroids if infective origin is ruled out. Taper as medically indicated.
	Hold treatment until recovery to ≤ Grade 1. May restart protocol treatment within 28 days at a reduced dose (by one level) if evidence of clinical benefit.
	Subjects will be withdrawn from the study if they fail to recover to ≤ Grade 1 within 28 days.
Grade 4	Prescribe corticosteroids if infective origin is ruled out. Taper as medically indicated.
	Discontinue treatment.
	Stomatitis ¹
Grade 1	Use conservative measures such as non-alcoholic mouth wash or salt water (0.9%) mouth wash several times a day until resolution

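### The fever limit in the febrile neutropenia DLT is printed as 101°F/38.5°C, but these are two different temperatures (101°F is 38.3°C; 38.5°C is 101.3°F)

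*Combined protocol and SAP*

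**What the plan says.** Section 3.2, Table 2, lists among the hematologic DLTs "Febrile neutropenia (ANC $< 1.0 \times 10^9$ /L" together with "fever $> 101^\circ F/38.5^\circ C". The two temperatures are separated by a slash, as one limit expressed in two units. The same section adds "All DLTs will be assessed by the investigator using CTCAE v5 criteria (NCI 2018"), but the protocol does not reproduce a CTCAE temperature limit.

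Section 3.2 also states what the DLT count is for: "for the purposes of dose cohort escalation/de-escalation, expanding a dose cohort, and determining the RP2D". Table 1 in Section 3.1.2 turns the count into action. For Cohort 1 after one DLT in the first three subjects and expansion to six, it reads "if no additional DLT, begin Phase 2 at Cohort 1 dose; if 1 or more additional DLTs, de-escalate to Cohort -1".

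The only other place where fever is paired with neutropenia is Table 3 in Section 5.6.1, a dose-interruption rule for "Grade 3 ANC with an oral temperature of at least 38.5°C". That rule is in Celsius only.

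**The concern.** If the two printed temperatures are not equal, the DLT criterion is really two criteria, and the plan does not choose between them. A subject could then be counted or not counted depending on the scale in which the temperature was read or recorded. An in-band case would have to be settled after the event was known, when the answer might already fix the cohort decision.

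The design is sensitive to single events:

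- **Cohort 1:** 0/3 means escalate, while 1/3 means add three subjects. After expansion, 1/6 means start Phase 2, while 2/6 means de-escalate.
- **Cohort -1:** a second DLT among six ends the study.
- **Phase II:** Section 7.2.2 refers to Section 3.2 for the DLTs counted against its boundaries (4 in 6, 5 in 9, 6 in 12, 7 in 15). Section 8.7 counts events meeting the Phase I DLT definition at any time. The ambiguity therefore carries past dose finding.

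**Working it through.** **Inputs.** The fever limit is 101°F and 38.5°C in the same cell, and the neutrophil limit is ANC < 1.0 x 10^9/L (both Section 3.2, Table 2). The related rule uses at least 38.5°C (Section 5.6.1, Table 3). No febrile neutropenia was seen in 55 NHL patients on everolimus 10 mg alone (Section 1.3.2).

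**1. Try to reproduce the printed pair.**

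- Fahrenheit to Celsius: (101 - 32) x 5/9 = 38.33°C, which rounds to 38.3 at one decimal, not 38.5.
- Celsius to Fahrenheit: 38.5 x 9/5 + 32 = 101.3°F.

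The pair is not reproduced. Rounding 38.33 to the nearest half degree would give 38.5, but the protocol states no such rounding.

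**2. Width of the disputed band.** 38.5 - 38.33 = 0.17°C; 101.3 - 101.0 = 0.3°F.

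**3. Which readings are affected** (ANC < 1.0 x 10^9/L, no other Table 2 criterion met):

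| Peak temperature | Above 101°F? | Above 38.5°C? |
|---|---|---|
| 38.3°C (100.94°F) | no | no |
| 38.4°C (101.12°F) | yes | no |
| 38.5°C (101.30°F) | yes | no |
| 38.6°C (101.48°F) | yes | yes |

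On a thermometer reading to 0.1°C, two values, 38.4 and 38.5, are classified differently. On one reading to 0.1°F, the values are 101.1, 101.2 and 101.3.

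**4. Does anything else in the protocol settle it?** No section names a governing unit. The CTCAE reference does not help, because Table 2 prints its own limit and no CTCAE limit is quoted. Table 3 uses 38.5°C, but for dose interruption rather than DLTs. It suggests the intended value without correcting Table 2. The fever of over 100.4°F used for B symptoms (Sections 3.3 and 7.6) is 38.0°C and serves a different purpose.

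**5. How often it might matter.** The documents give no in-band rate. For scale, Section 1.3.2 reports that "febrile neutropenia was not observed and 8/55 discontinued therapy because of adverse events". With 0 of 55, the one-sided 95% upper limit for all febrile neutropenia is 1 - 0.05^(1/55) = 5.3%, and the band would be only part of that. Those patients had twice the everolimus dose and no itacitinib, so the figure does not bound the rate here.

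Taking an in-band rate r of 0.5% to 2% purely as an assumption, the chance of at least one such subject is 1 - (1 - r)^n:

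| r (assumed) | n = 3 | n = 6 |
|---|---|---|
| 0.5% | 1.5% | 3.0% |
| 1% | 3.0% | 5.9% |
| 2% | 5.9% | 11.4% |

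This is the chance that an ambiguous case occurs, which is larger than the chance that a dose decision changes. In Cohort 2 or Cohort -1, for example, moving from 0/6 to 1/6 still leads to Phase 2 at that dose.

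**The case against.** The strongest reply is that this is a rounding slip with little reach.

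- **Review of cases.** Events are not classified by thermometer alone. Section 3.2 excludes those with a clear alternative explanation, with investigator and sponsor judgement, and disease-related fever is expected in this population. This exception would remove some borderline cases. It applies equally under either unit, however, so it does not say which limit holds for the cases that remain.
- **Neutrophil margination.** The note after Table 2 says that neutropenia must persist for 3 days after itacitinib is held. It can be read as narrowing the neutropenia DLTs further, but it does not name febrile neutropenia. Table 2 attaches the recovery condition to the Grade 4 neutropenia line only.
- **Single centre.** One site makes inconsistent use of units less likely. That reduces the risk but does not supply the missing rule.
- **Frequency.** The assumed rates of 0.5% to 2% have no basis in the documents, and the resulting percentages overstate the effect on decisions. Both points stand. The percentages show scale only, and the conclusion does not depend on them.
- **Table 3.** Table 3 says at least 38.5°C and Table 2 says above it. If Table 2 is set to above 38.5°C, a reading of exactly 38.5°C will still meet one rule and not the other. This is true. The tables serve different purposes, so the difference can stand, and it does not affect the unit mismatch.

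**Conclusion.** The concern holds. The printed Fahrenheit and Celsius limits differ by 0.17°C (0.3°F), and the protocol gives no means of choosing between them. The conversion is exact and rests on no assumption. The practical effect is small: it needs ANC below 1.0 x 10^9/L, a peak temperature inside the band, no other DLT criterion met and no clear alternative cause. How often that would happen with this combination is unknown. Sample size, alpha, power and the CR analysis are untouched. The point is worth correcting because the figure belongs to an operative safety criterion on which one event can turn a cohort decision, not because a changed decision is likely.

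**What to change.** Give Table 2 one limit with matching units. Above 38.5°C (101.3°F) is the natural choice, since 38.5°C is also the temperature in Table 3 and is probably what was meant. If the more cautious limit is intended, print above 38.3°C (101°F). Table 3 can stay as it is. If the authors want the two tables to agree at exactly 38.5°C as well, they can align the inequality in the same edit.

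The cost is one figure in Table 2, with no recalculation, redesign or added data collection. If any subject has already had a neutropenic fever with a peak above 38.33°C and up to 38.5°C, record how that event was classified.
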